12.2.9.3. Hypoglycemic Events

The incidence, rate per 30 days and rate per year of hypoglycemic episodes (total, severe, and nocturnal as defined in Section 9.10) will be summarized by treatment at baseline, titration, maintenance, and overall study periods and at endpoint. The rate per 30 days between 2 visits is defined as the total number of episodes between the visits divided by the actual number of days between the visits, and then multiplied by 30 days.

The proportion of patients (with at least 1 hypoglycemic event (total, severe, nocturnal, and others) or incidence during the study will be summarized (counts and percentages) and analyzed using Fisher's exact test or the Pearson's chi-square test for the FAS population.

The rate of hypoglycemic episodes per 30 days and per year (total, severe, nocturnal, and others) will be analyzed at baseline, titration, maintenance, and overall study periods and at endpoint using the Wilcoxon test. In addition, the hypoglycemia rates will also be analyzed using a negative binomial model for the FAS population with terms for treatment, baseline HbA1c, prestudy treatment, and prestudy metformin or acarbose usage. The offset variables are log of patient's treatment duration/30 and log of patient's treatment duration/365.25 for the models analyzing hypoglycemia rate per 30 days and per year, respectively.

In addition, the total number of patients with at least 1 hypoglycemic episode divided by the total extent of exposure in patient-years will be calculated for the overall study period and summarized descriptively for each treatment group for total, severe, nocturnal, documented symptomatic, and asymptomatic hypoglycemia definitions only. Listings of hypoglycemic episodes will be presented by visit for each subject.

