The baseline is Visit 2. If baseline data are missing, the last measurement taken prior to this visit will be used for the baseline measurement.

The last visit for the 24-week treatment study is Visit 13. If the Visit 13 measurement is missing, the last post-baseline value will be carried forward to create the 24-week endpoint value using the last-observation-carried-forward (LOCF) methodology. If there are no measurements after Visit 2 (date of randomization), the 24-week endpoint values will be considered missing. If the baseline value is missing or a patient only has a baseline value with no follow-up values, then the patient will not be included in the efficacy analyses. The LOCF methodology will be utilized in the endpoint analyses using analysis of covariance (ANCOVA) of HbA_{1c}, laboratory chemistry and hematology, as well as analysis of hypoglycemia (rate and incidence) and insulin antibodies.

Unless otherwise noted, the analysis of the continuous secondary efficacy and safety variables (SMBG at each time point and summaries of SMBG, weight, dose, and vital signs) will be performed using the same mixed model repeated measures (MMRM) methodology for the primary efficacy analysis with the baseline value of the response variable added as a covariate with the FAS population. Continuous laboratory measures will be analyzed using the ANCOVA model.

Unless otherwise noted, the analysis of categorical variables to compare the 2 treatments will be performed using Fisher's exact test or Pearson's chi-square test.

Values for the 7-point self-monitored blood glucose (SMBG) blood glucose profiles will be averaged over the two 7-point SMBG profiles obtained during 2-week period prior to each office visit (as specified in Protocol Section 7.2.3). For the average blood glucose calculation for a specific time point, if only 1 of 2 days of data is collected, then the value of the 1 day will be used. If 2 days of data are collected, then the average of the 2 days will be used. If more than 2 days of data are collected then choose the 2 according to the ranking first by the number of non-missing blood glucose measurements and then by day closest to the visit day. The handling of missing data for the ITSQ questionnaire is specified in Section 5.2.10.

Visits for laboratory data will be handled by conventions in the Lilly diabetes white paper (Standardization of Derivations for Efficacy Lab Variables).

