Pseudo-hypoglycemia: an event during which the person with diabetes reports any of the typical symptoms of hypoglycemia with a measured plasma glucose concentration >70 mg/dL (> 3.9 mmol/L) but approaching that level.

Besides the hypoglycemic categories listed above, total hypoglycemic event will be defined as follows:

Total hypoglycemic event: any event which is either documented symptomatic hypoglycemia, asymptomatic hypoglycemia, probable symptomatic hypoglycemia or severe hypoglycemia.

For each category of hypoglycemia event, the incidence, the number of hypoglycemic events per patient, the rate of hypoglycemic events per year (that is, the number of hypoglycemic episodes per patient per patient year [365.25 days]) will be calculated. These measures will be summarized at baseline, titration, maintenance, and overall study periods and at endpoint.

The proportion of patients with at least 1 hypoglycemic event (total, severe, nocturnal, and others) or incidence during the study will be summarized (counts and percentages) and analyzed using Fisher's exact test or the Pearson's chi-square test for the FAS population.

Logistic regression will be used as a sensitivity analysis of the incidence of hypoglycemia. The model will have presence or absence of hypoglycemia as the dependent or response variable and treatment, baseline HbA_{1c}, pre-study treatment (Lantus®-bolus, other basal-bolus, premixed insulin), and pre-study metformin or acarbose usage (metformin only, acarbose only, or neither) as the independent terms in the model.

The rate of hypoglycemic episodes per year (total, severe, nocturnal, and others) will be analyzed at baseline, titration, maintenance, and overall study periods and at endpoint using the Wilcoxon test. In addition, the hypoglycemia rates will also be analyzed using a negative binomial model for the FAS population with terms for treatment, baseline HbA_{1c}, pre-study treatment (Lantus®-bolus, other basal-bolus, premixed insulin), and pre-study metformin or acarbose usage (metformin only, acarbose only, or neither).

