For each subgroup listed above, the change in weight from baseline to 24-week will be analyzed using the same methodology as the subgroup analysis of HbA_{1c}.

Additional subgroup analyses will be carried out on selected safety outcomes:

- a) total, severe or nocturnal hypoglycemia at 24-week endpoint and for the overall 24-week period (rates and incidence)
- b) treatment-emergent antibody response (TEAR) at 24-week endpoint and for the overall 24-week period
- c) detectable insulin antibodies at 24-week endpoint and for the overall 24-week period
- d) categories of adverse events:
 - treatment-emergent adverse events (TEAEs) (overall incidence and preferred terms with $> 5\%$ incidence)
 - TEAEs related to study drug (overall incidence)
 - special topic assessment of allergic events (overall incidence)
 - injection site reactions (overall incidence)
 - serious adverse events (overall incidence)

For rates and incidence of hypoglycemia (total, nocturnal, severe) and categories of adverse events, the same set of 11 subgroups used to analyze change in HbA_{1c} and change in weight will be analyzed.

For each categorical safety outcome and subgroup listed above, the proportion of patients with an event will be compared between treatments for the FAS. Within each subgroup, treatments will be compared using the Mantel-Haenszel test and the odds ratio and p-value from this test will be reported. The homogeneity of the odds ratios across subgroups will be assessed using the Breslow-Day test.

For the 11 subgroups listed above, the rate of total, severe or nocturnal hypoglycemia per year at the 24-week endpoint and for the overall 24-week period will be analyzed. Within each subgroup, treatments will be compared using the negative binomial (NB) model with treatment as the only factor. The NB mean for each treatment and their ratio with corresponding 95% confidence interval will be presented. Additionally, within each subgroup the rates will be compared using the Wilcoxon test. The significance of the subgroup-by-treatment interaction will be evaluated using a negative binomial model with factors treatment, subgroup and treatment-by-subgroup interaction. The negative binomial model will be implemented using the SAS PROC GENMOD with natural logarithm of exposure time (in days) as an offset variable. The above subgroup analysis will be performed and p-values will be provided if there are at least a total of 20 events in the combined treatment groups.

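### Carrying hypoglycemia incidence forward to the 24-week endpoint mixes observation windows of unequal, undefined length with no adjustment for exposure

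*SAP*

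**What the plan says.** SAP 5.2.1 sets the endpoint rule: "If the Visit 13 measurement is missing, the last post-baseline value will be carried forward to create the 24-week endpoint value". It then names the analyses to which the rule applies, ending with "as well as analysis of hypoglycemia (rate and incidence) and insulin antibodies".

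The endpoint is reported separately from the study periods. On incidence, event counts and yearly rates, SAP 5.2.11.2 says: "These measures will be summarized at baseline, titration, maintenance, and overall study periods and at endpoint". SAP 5.2.12 adds subgroup analyses of "total, severe or nocturnal hypoglycemia at 24-week endpoint and for the overall 24-week period (rates and incidence").

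The only definition tied to an interval is in Protocol 12.2.9.3, where the 30-day rate between two visits "is defined as the total number of episodes between the visits divided by the actual number of days between the visits", times 30. The SAP's yearly rate is "the number of hypoglycemic episodes per patient per patient year [365.25 days"]. Incidence is a plain yes/no: "The proportion of patients with at least 1 hypoglycemic event (total, severe, nocturnal, and others) or incidence during the study" is compared by Fisher's exact or Pearson's chi-square test. The logistic sensitivity model has terms for treatment, baseline HbA1c, pre-study treatment and metformin or acarbose use, but none for time at risk. Neither document says which interval produces the endpoint hypoglycemia value.

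**The concern.** HbA1c, laboratory values and antibody binding are levels read at a visit, so carrying the last one forward at least yields the same kind of quantity for everyone. Hypoglycemia is a count over an interval, and the interval changes during the trial. Attachment 1 collects episodes at Weeks 1, 2, 3, 4, 5, 6, 8, 10, 12, 18 and 24 and at early discontinuation. A completer's last interval is 6 weeks. A patient who leaves during titration may carry forward a result from 1 or 2 weeks, or from a few days. A shorter window gives less chance of an event, yet the tests treat the two results as the same outcome.

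Hypoglycemia is a named secondary safety objective in an open-label trial. If dropout differs between arms, part of any endpoint difference in incidence would reflect length of observation, and events from titration would appear under a Week 24 label.

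**Working it through.** **The plan's own figures.** The documents give no figure for endpoint hypoglycemia. The sample size, which supplies the dropout assumption, reproduces: 2 × (1.960 + 0.842)² × 1.05² / 0.40² = 108.2, so 109 per arm; 109 / 0.85 = 128.2, so 129 per arm and 258 in total.

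**Inputs.** From the documents: the visit schedule and 15% dropout. Assumed: events follow a gamma-Poisson model with shape 1; the rate r is constant over 24 weeks and equal in both arms; dropout is uniform over days 7 to 168 (23 weeks); dropout is 10% in one arm and 20% in the other. The documents give no total hypoglycemia rate, so r is taken over a range.

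**Step 1: incidence by window.** P(d) = m / (1 + m), with m = r × d / 365.25.

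| Events per year | 7 days | 14 days | 42 days |
|---|---|---|---|
| 40 | 43.4% | 60.5% | 82.1% |
| 10 | 16.1% | 27.7% | 53.5% |
| 3 | 5.4% | 10.3% | 25.6% |
| 0.1 | 0.2% | 0.4% | 1.1% |

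**Step 2: mean incidence S carried forward by dropouts.** The undefined window can be read in four ways. At 10 per year:

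- *All visits, last completed interval.* Of the 23 exit weeks, 7 carry a 1-week window, 10 a 2-week and 6 a 6-week window: (7 × 16.1 + 10 × 27.7 + 6 × 53.5) / 23 = 30.9%.
- *Clinic visits, last completed interval.* Exits in Week 1 to 2 have none. Of the other 22 weeks, 10 carry 2 weeks and 12 carry 6 weeks: (10 × 27.7 + 12 × 53.5) / 22 = 41.8%. Here 12/22 = 55% of these dropouts have the same window length as a completer.
- *All visits, interval closed by an early discontinuation visit.* The mean of P over an interval of L days is 1 − ln(1 + M)/M, with M = r × L / 365.25. This is 8.5%, 15.4% and 33.4% for L = 7, 14 and 42. Then (5 × 8.5 + 6 × 15.4 + 12 × 33.4) / 23 = 23.3%.
- *Clinic visits, interval closed by an early discontinuation visit.* Exits in Week 1 to 2 average (14 × 15.4 − 7 × 8.5) / 7 = 22.3%. Then (1 × 22.3 + 4 × 15.4 + 18 × 33.4) / 23 = 29.8%.

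**Step 3: between-arm bias.** Bias = (0.20 − 0.10) × (S − P(42)), the higher-dropout arm minus the other, in percentage points.

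| Events per year | All visits, early visit closes | All visits, completed | Clinic, early visit closes | Clinic, completed |
|---|---|---|---|---|
| 40 | -3.4 | -2.1 | -2.4 | -1.0 |
| 10 | -3.0 | -2.3 | -2.4 | -1.2 |
| 3 | -1.6 | -1.3 | -1.3 | -0.7 |
| 0.1 | under 0.1 in size | under 0.1 | under 0.1 | under 0.1 |

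**Step 4: equal dropout.** With 15% in each arm at 10 per year, both arms fall by 0.15 × (53.5 − 41.8) = 1.8 points to 0.15 × (53.5 − 23.3) = 4.5 points. The difference between arms is zero and the false-positive rate stays at 5%.

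**Step 5: false positives, illustrative worst case.** If every dropout carries a 7-day window, 10% versus 20% dropout with 129 per arm raises the false-positive rate to 7.6% to 11.3% for 5 to 40 events per year (normal approximation).

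**Step 6: rates.** Dividing by days leaves the expected rate unchanged at a constant r. Precision does change. One event annualises to 365.25/7 = 52.2, 365.25/14 = 26.1 or 365.25/42 = 8.7 per year, and at 20 per year the Poisson SD is 32.3, 22.8 or 13.2.

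**The case against.** A reader might infer several stronger points that the documents do not support.

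- *That rates from short windows are treated as 6-week values.* They are not. The protocol divides the "total number of episodes between the visits divided by the actual number of days between the visits" and the SAP works in patient-years. What remains for rates is unequal precision, coarse Wilcoxon ranks, and titration-phase data labelled Week 24.
- *That the short window is certain.* It is inferred from the schedule. Protocol 7.2.2.3 has telephone-visit episodes entered in the eCRF at the next office visit, which favours clinic visits as the bounds, and that reading gives the smaller biases.
- *That the arms will differ.* Bias needs unequal dropout or unequal timing. The protocol plans one common 15%; the 10% versus 20% split is assumed. If event rates differ between titration and maintenance, the size and even the direction could change, and Protocol 7.2.1 expects most dose changes in Weeks 0 to 6.
- *That the error repeats in every category and subgroup.* SAP 5.2.11.2 attaches its Fisher or chi-square test to incidence during the study; the test at endpoint follows only from the general default in SAP 5.2.1. The explicit endpoint comparison of incidence is in SAP 5.2.12, by Mantel-Haenszel, for total, severe and nocturnal events, and the subgroups depend on cell size.

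It is also fair that titration, maintenance and overall-period results are planned, and that no primary or gated claim rests on the endpoint row. All of these limits stand. They do not remove the central fault: the SAP explicitly carries incidence forward, and no incidence test allows for window length.

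**Conclusion.** The point holds for incidence. Followed as written, the SAP gives a Week 24 incidence that combines windows of different, undefined length. The between-arm bias of about 1 to 3 points at 10 to 40 events per year is conditional on a constant rate, the shape-1 model and a 10% versus 20% dropout split. It is negligible for rare events and zero between arms when dropout and its timing are equal.

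For rates there is no bias in expectation at a constant rate. One related gap does matter: SAP 5.2.12 uses log exposure time in days as the negative binomial offset without saying whether, for the endpoint rate, this means days in the endpoint window or total exposure. Total exposure would mis-scale an endpoint count.

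This is a minor point on a secondary safety analysis. The primary HbA1c analysis, its error rate and the 258 patients are unaffected.

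**What to change.** In the SAP:

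1. Remove hypoglycemia from the LOCF list in 5.2.1.
2. Define the endpoint window for hypoglycemia as the observed Visit 12 to Visit 13 interval.
3. Analyse endpoint rates on observed counts with log(days in that window), not total exposure, as the offset, and say so in 5.2.12.
4. Label endpoint incidence as descriptive, in patients observed in that window, and note that this conditions on remaining in the study.
5. Base between-arm hypoglycemia conclusions on the overall-period negative binomial analysis in all FAS patients with a log-exposure offset. SAP 5.2.11.2 should state the offset; at present it is given for the main model only in Protocol 12.2.9.3.

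The cost is SAP wording and programming specifications, with no new data. The downside is that early leavers are absent from the endpoint table. That may introduce selection, since hypoglycemia can itself influence who stays, which is why the endpoint figure should be descriptive only. Those patients remain in the overall-period analysis.

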7.2.2.4. Study Visits (Visit 3 to Visit 13 or Early Discontinuation)

Patients will come to the investigator site at 2-week intervals between Visit 2 and Visit 8. From Visit 8 to Visit 13, patients will come to the clinic at 6-week intervals. Visit 801 is a 4-week follow-up clinic visit ([Attachment 1](#)).

Between Visit 2 and Visit 4 and Visit 4 and Visit 6, Visit 6 and Visit 8, Visit 8 and Visit 11, there are telephone visits (Visits 3, 5, 7, 9 and Visit 10), which are described separately (Section 7.2.2.3).

The following activities will occur during Visits 3 to Visit 13 or Early Discontinuation (ED):

- study diaries collected and reviewed for BG levels, episodes of hypoglycemia, injection-site skin reactions, and insulin self-administration (Section [7.2.2.2.1.1](#))
- distribute study diaries (not completed at ED)
- dispense glucose-meter supplies as needed (not completed at ED)
- dispense study drug/device at Visits 8, 11, and 12 (not completed at Visit 13 or at ED)
- collection of blood sample for HbA1c assessment to determine efficacy of treatment values for each patient at Visits 8, 11, 12, and Visit 13 (or ED)
- transfer data from study diaries into eCRF (including previous day's insulin dose from last telephone visit)
- collect study drug at Visits 8, 11, 12, and Visit 13 (or ED)
- the previous day's insulin dose
- titration of insulin/adjust insulin dose as needed during visits (See [Attachment 5](#); not completed at Visit 13 or at ED)
- assessment of vital signs and body weight
- blood sampling for chemistry and hematology at Visit 13 or ED
- inquiries of AEs
- inquire about use of concomitant medications
- collection of blood sample to determine generation of anti-glargine antibodies at Visits 4, 8, 11, and Visit 13 (or ED)
- collection of serum samples for biomarker analyses during Visit 8 and Visit 13
- Health outcomes of the study will be measured as reflected in responses to ITSQ administered to the patients during Visit 13, (or ED), as indicated in the Study Schedule ([Attachment 1](#)).

In addition to the daily BG monitoring, patients will be required to complete the following, which are reviewed and/or transferred to eCRF during Visit 3 to Visit 13 or ED:

- 7-point SMBG profiles (described in Section [7.2.3](#)) on 2 separate days in the 1-week period prior to all investigator-site visits (or at ED) (preferably most recent readings).

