7.2.3. Blood Glucose Monitoring Plan

Patients will be provided with glucometers and corresponding glucose test strips so they can obtain SMBG values. Blood glucose values will be utilized to guide insulin titration dosing, to determine hypoglycemia (as specified in the protocol), and to ensure that uniform data are collected.

Throughout the study, patients will be expected to check their fasting blood glucose (FBG) values daily to assess the need for basal insulin-dose adjustments ([Attachment 5](#)). They will also be instructed to record results of 4- and 7-point SMBG values in the study diaries, as described below, so they can be shared and help inform the investigators who will direct insulin-dose adjustments, as needed, to help patients achieve glycemic targets (HbA1c <7%, preprandial BG 79 to 126 mg/dL [4.4 to 7.0 mmol/L]) while minimizing/avoiding hypoglycemia. For consistency, the first recorded BG value for each profile should be a premorning meal value followed by the other specified BG values throughout the day.

- Patients will be instructed to complete 3 separate 4-point SMBG values (once before each meal and at bedtime) (preferably most recent readings) during the period prior to each telephone visits. Four-point SMBG values will be reported during telephone visits and will be recorded at the subsequent office visit or Visit 801.
- Patients will be instructed to complete 2 separate 7-point SMBG profiles in the 1-week period prior to each office visit from Visit 2 to Visit 13 (or at ED) (preferably most recent readings). At Visit 801, only 4-point SMBG is required to be collected. The SMBG profiles will consist of:
 - before the morning meal, midday meal, and evening meal; 2-hour postprandial measurements for the morning, midday meal, at bedtime and 3 am.

Throughout the study, patients will be expected to routinely check their fasting, premeal, and bedtime BG values daily to help assess the need for dose adjustments and to guide dosing of the mealtime/fast-acting insulin lispro ([Attachment 5](#)). Patients may be requested by investigators (as they deem necessary) to perform more intensive self-monitoring, if clinically indicated. Both 4-point and 7-point SMBG values will be recorded in the diaries and transcribed into the eCRF at the office visit ([Attachment 1](#) and [Attachment 5](#)).

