Telephone Visit			X		X		X		X	X					
Clinic Visit	X	X		X		X		X			X	X	X	X	X
Telephone Visit 4-point SMBG				X		X		X			X				
Lab Assessments															
Chemistry	X												X		X
Hematology	X												X		X
Pregnancy Screen ^h	X ^h														
ECG (local)	X														
HbA1c	X	X						X			X	X	X		X
Serum Samples for Biomarkers (Fasting) ⁱ		X ⁱ						X ⁱ					X ⁱ		X ⁱ
Anti-Glargine Antibody Titer		X		X				X			X		X		X
Fasting Serum Glucose ⁱ		X ⁱ											X ⁱ		X ⁱ
Other Transfer Data to eCRF (InForm™)															
Administer the ITSQj.k		Xj											Xj		Xj.k

Abbreviations: BG = blood glucose; DBP = diastolic blood pressure; ECG = electrocardiogram; eCRF = electronic case report form; ED = early discontinuation; HbA_{1c} = hemoglobin A_{1c}; HR = heart rate; ITSQ = Insulin Treatment Satisfaction Questionnaire; SBP = systolic blood pressure; SMBG = self-monitored blood glucose.

* Telephone visit.

Patients who discontinue early from the study will complete Visit 801.

- a For visit window purposes, the visit will end on the last day when the patient completes a study procedure or assessment. Visits should occur within the visit intervals indicated. The timing of visits (including allowable deviations) should be based on time postrandomization.
- b Adverse events, hypoglycemic episodes, concomitant medications, and the last three available 4-point SMBG profiles reported at telephone visits should be recorded on the eCRF at the next office visit. The 4 points are: before morning, mid-day, evening meals, and at bedtime.
- c Patients should perform two 7-point SMBG profiles during the 1-week period prior to these visits. The 7 points are: before the morning meal, midday meal, and evening meal; 2-hour postprandial measurements for the morning, midday meal, at bedtime and 3 am. In some instances (for example, between Visit 2 and Visit 3), some readings of the 7-point SMBG could overlap with those taken for the 4-point SMBG.
- d Training should include instruction on glucose self-monitoring and the use of the glucose meter, record-keeping, hypoglycemia/marked hyperglycemia recognition and treatment, injection technique and device use, diet, and exercise. Additional training activity should be provided as needed throughout the study.
- e Dispense glucose meter supplies as needed; may not be at every visit.
- f Study sites will retain study diaries.
- g Transfer values from the study diary if available.

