- b. Prestudy basal-bolus insulin regimen (BID basal + TID premeal) (1:1 conversion of bolus insulin and 80% of pre-study basal insulin):

NPH 10U (breakfast), 10U (dinner) + Lispro 6U (breakfast), 6U (lunch), 6U (dinner)

Will switch to:

LY2963016 (or Lantus®) $(10U+10U)*80%=16U$ QD (daytime or evening/bedtime at the discretion of investigator) + Lispro 6U (breakfast), 6U (lunch), 6U (dinner).

- c. Prestudy premixed insulin BID

In past 3 days, Humulin 70/30 18U (breakfast), 12U (dinner), total daily insulin dose: 30U

Will switch to:

LY2963016 (or Lantus®) $30U*40%=12U$ QD (daytime or evening/bedtime at the discretion of investigator) +6U for each meal ($30U*60%=18U$, equally divided into 3 meals), or appropriate adjustment at discretion of the investigators.

3. Insulin dose adjustments are mostly based upon SMBG levels. Four-point SMBG values will be reviewed during the telephone visit period and be recorded in the eCRF during the next investigator-site visit. In addition, 7-point SMBGs are also recorded during the 1-week period preceding office visits. The patient's SMBG results are to be used by the investigator to inform dose adjustments for a particular insulin dose (that is, adjustment based on glucose pattern or trends), as represented in Table A5.1.

Table A5.1. Overview of Scenarios with Different Blood Glucose Levels and Corresponding Insulin-dose Adjustments*

Time	BG <80 mg/dL (<4.4 mmol/L)	BG >140 mg/dL (>7.8 mmol/L)
AM	Decrease Basal or Bedtime insulin	Increase Basal or Bedtime insulin
Pre-midday meal	Decrease AM lispro	Increase AM lispro
PM	Decrease Pre-midday meal lispro	Increase Pre-midday meal lispro
	Bedtime BG <100 mg/dL (<5.5 mmol/L)	Bedtime BG >160 mg /dL (>8.9 mmol/L)
BEDTIME	Decrease PM lispro	Increase PM lispro

Abbreviations: BG = blood glucose.

* Adapted from Staged Diabetes Management.

Additional BG monitoring may be requested by the investigator while optimizing insulin doses. The investigator may adjust the insulin dose every 3 to 4 days (twice per week, [for example, via instructions to patient]) when appropriate, based on the patient's glycemic needs as reflected by SMBG measurements, and after the investigator has evaluated the role of diet and exercise on the resulting BG measurements.

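### The SAP takes 7-point SMBG profiles from a 2-week window and credits it to Protocol 7.2.3, which specifies 1 week; early SMBG values may then reflect an earlier insulin dose

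*SAP*

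**What the plan says.** SAP 5.2.1 (General Considerations) averages each patient's two 7-point profiles "obtained during 2-week period prior to each office visit (as specified in Protocol Section 7.2.3"). If a time point has data from only one day, that day is used. If more than two days are available, two are chosen by "ranking first by the number of non-missing blood glucose measurements and then by day closest to the visit day".

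Protocol 7.2.3 reads differently: "Patients will be instructed to complete 2 separate 7-point SMBG profiles in the 1-week period prior to each office visit". The rest of the protocol agrees with it:

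- Section 7.2.2.4: "on 2 separate days in the 1-week period prior to all investigator-site visits".
- Attachment 1 (Study Schedule), footnote c: "Patients should perform two 7-point SMBG profiles during the 1-week period prior to these visits".
- Attachment 5: "7-point SMBGs are also recorded during the 1-week period preceding office visits".

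No current protocol text gives 2 weeks as the window for 7-point profiles.

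The profiles feed a named secondary objective, the comparison of 7-point SMBG at baseline and Weeks 2, 4, 6, 12, 18 and 24. They also feed the derived measures in SAP 5.2.8: daily mean, premeal and postprandial means, the bedtime-to-3 AM excursion, and the SD used for within-patient variability.

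**The concern.** The SAP cites a source for its window, and the source says something else. A programmer working from the SAP and one working from the cited section would select different data.

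The difference matters most while insulin is being titrated. Office visits are 2 weeks apart up to Week 6, with a telephone visit at which doses can be changed between each pair. A value labelled Week 2, 4 or 6 should describe glucose control shortly before that visit. With a 14-day window it may come partly or wholly from before the most recent scheduled adjustment.

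**Working it through.** The plan states no figure that depends on this window, so there is none to reproduce. The check compares the two windows with the visit calendar.

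**Inputs**

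- Window length L: 14 days (SAP 5.2.1) or 7 days (Protocol 7.2.3).
- Office visits after baseline: Visits 4, 6, 8, 11, 12 and 13 at Weeks 2, 4, 6, 12, 18 and 24 (Attachment 1).
- Telephone visits with possible dose adjustment: Visits 3, 5, 7, 9 and 10 at Weeks 1, 3, 5, 8 and 10 (Protocol 7.2.2.3, Attachment 1). Doses can also be adjusted at office visits before Visit 13.
- First study insulin: the day after Visit 2 (Protocol 9.1).

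**Formula.** Nominal day = 7 × week. Window start = visit day − L. A contact is inside the window if start < contact day < visit day.

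| Visit | Day | 7-day window | Contact inside | 14-day window | Contact inside |
|---|---|---|---|---|---|
| 4 | 14 | 7 to 14 | none (Visit 3 is on the first day) | 0 to 14 | Visit 3, day 7 |
| 6 | 28 | 21 to 28 | none (Visit 5 is on the first day) | 14 to 28 | Visit 5, day 21 |
| 8 | 42 | 35 to 42 | none (Visit 7 is on the first day) | 28 to 42 | Visit 7, day 35 |
| 11 | 84 | 77 to 84 | none | 70 to 84 | none (Visit 10 is on the first day) |
| 12 | 126 | 119 to 126 | none | 112 to 126 | none |
| 13 | 168 | 161 to 168 | none | 154 to 168 | none |

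At Visits 4, 6 and 8 the 14-day window equals the full interval since the previous office visit (14 of 14 days), and its first half precedes the intervening telephone contact. The 7-day window covers only the second half.

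**How an older profile gets in.** There are three routes, and each needs a recorded profile 8 to 14 days old:

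1. It is the only one available, and is used alone.
2. It is one of two, and is averaged with a recent one.
3. There are more than two, and it has more non-missing points than a recent one. Completeness ranks first, so the older profile is kept.

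**Start of treatment.** At nominal timing the Visit 4 window opens on day 0, before the first study dose. If Visit 4 is e days early, the 14-day window starts on day (14 − e) − 14 = −e and the 7-day window on day (14 − e) − 7 = 7 − e. One day early gives −1 against 6; three days early gives −3 against 4. Three days is an assumption, because the allowable-deviation row of the Study Schedule could not be read column by column in the text used here. A pre-treatment profile would count at Week 2 only if profiles are assigned to visits by date, which the SAP does not state.

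**The case against.** The strongest reply is that data collection limits the harm. Patients are told to do both profiles in the week before the visit, preferably using the most recent readings, so the second week of the window will often be empty. This stands: the window length is not itself an effect on any estimate, and the documents give no share of patients with older profiles. But the SAP has a rule for more than two days of data, so it expects extra profiles, and a rule that contradicts its own citation still needs correcting.

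A reader might infer four stronger things that the documents do not support.

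- **That baseline profiles will be analysed as Week 2 data.** Baseline profiles are reviewed and transferred to the eCRF at Visit 2, when the Visit 1 diary is collected and a new one issued. Reusing them would require reassignment by date. The SAP neither states nor excludes this, so it is a possibility only.
- **That the wide window pulls the arms together.** Attenuation requires a true difference in SMBG between the arms. Both follow the same titration guidance, and SAP 5.1.2.1 expects similar mean responses. SMBG has no noninferiority margin and is outside the gatekeeping.
- **That a 1-week window guarantees current-dose data.** Attachment 5 allows adjustment every 3 to 4 days, and a telephone visit held a day or two late would fall inside even a 7-day window. One week reduces the mixing without removing it.
- **That ranking completeness ahead of closeness is an error.** It is defensible for a seven-point mean and SD. It causes trouble here only because the window is wide.

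**Conclusion.** The point holds as a wrong analysis window with a wrong cross-reference. SAP 5.2.1 gives 14 days where the section it cites, and three other protocol places, give 7. SAP 5.2.1 itself says that changes from the protocol's methods will be justified in the SAP or the study report; the SAP gives no justification here and presents 2 weeks as the protocol's rule.

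The size is modest. At nominal visit days, one scheduled dose-adjustment contact falls inside the 14-day window at each of Visits 4, 6 and 8, and none at Visits 11, 12 and 13; none falls strictly inside the 7-day window at any visit. The exposure is therefore mainly at Weeks 2, 4 and 6 and confined to secondary SMBG outcomes. The HbA1c noninferiority test, the reverse test and the sample size do not use these data. The number of patients affected cannot be derived from the documents.

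The textual mismatch is certain. The consequence depends on profiles 8 to 14 days old being recorded and, for pre-treatment profiles, also on assignment by date and an early Visit 4.

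**What to change.** In SAP 5.2.1, change the window from 2 weeks to 1 week before each office visit, so that it matches Protocol 7.2.3. The completeness-then-closeness ranking can stay and operate within that week. No separate rule requiring profiles to follow the first dose is needed for the case worked above: with a 7-day window, a Visit 4 three days early still looks back only to day 4.

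If the sponsor does intend 2 weeks for analysis, the SAP should say so, give the reason, and drop the attribution to the protocol.

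The cost is one phrase in the SAP and the matching programming specification, before database lock. The downside is small: a patient whose only profile is more than 7 days old has a missing value at that visit. A few more visit-level SMBG values may be lost, which the planned MMRM accommodates under missing at random.
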